#### **8.4 Other Analyses**

AUC/time based on Changes from Baseline in KOOS JR. Scores, NRS for Pain, and TUG test through 72 hours post-TKA (KOOS JR. and NRS for Pain only), 2 weeks post-TKA and 12 weeks post-TKA will be analyzed in the same manner as described in Section 8.2 for the AUC/time endpoints through 6 weeks post-TKA. AUC/time based on Changes from Baseline in ROM through 2 weeks post-TKA, 6 weeks post-TKA, and 12 weeks post-TKA will also be analyzed in this same manner.

Subject satisfaction data will be summarized by treatment group and visit (weeks 6 and 12) using descriptive statistics for both overall knee pain status since the beginning of the study and satisfaction with pain management following surgery and counts and percentages for overall knee pain status since the beginning of the study.

██████████ last NRS for Pain (both seated and with motion) reported as part of physical therapy will be summarized by treatment group using descriptive statistics.

For each post-baseline visit, p-values will be presented for the test of the null hypothesis that the true mean changes from baseline in NRS for Pain are equal for the two treatments versus the alternative hypothesis that they are not equal. It should be noted that this is an open label study and that these hypothesis tests of superiority are post-hoc and were not pre-planned in the protocol.

These analyses will be performed for the ITT Population.

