## 8.2 Secondary Effectiveness Endpoints

The secondary effectiveness endpoints are as follows:

1. AUC/time (see definition of AUC/time below) based on Changes from Baseline in KOOS JR. Scores through 6 weeks post-TKA.  
KOOS JR. Scores range from 0 (total knee disability) to 100 (perfect knee health).
2. AUC/time based on Changes from Baseline through 6 weeks post-TKA in NRS for Pain (both pain in the last 7 days and pain right now)  
NRS Pain ratings range from 0 (no pain) to 10 (worst pain imaginable).
3. AUC/time based on Changes from Baseline through 6 weeks post-TKA in Timed Get Up and Go (TUG) test.  
The TUG test measures, in seconds, the time it takes to raise from sitting, walk 10 feet, turn around, walk back and sit back down.

Change in KOOS JR. scores from the Baseline visit to each post-baseline visit will be calculated for each subject as:

$$\text{Change in KOOS JR. score} = \text{Post-Baseline Visit KOOS JR. score} - \text{Baseline Visit KOOS JR. score},$$

such that a positive value indicates an increase in the KOOS JR. score, while a negative value indicates a decrease. The first and key secondary effectiveness endpoint, AUC/time based on Changes from Baseline in KOOS JR. scores through 6 weeks post-TKA, is the area under the curve (AUC) of Change in KOOS JR. scores from the Baseline visit through the 6-week visit divided by the number of days from TKA until the 6-week visit. AUC will be calculated using the trapezoidal rule and the changes in the KOOS JR. score at the following time points: Baseline (change=0), 72 hours, 2 weeks, and 6 weeks post-TKA. Scoring instructions for the KOOS JR. English Version 1.0 are provided in Appendix 1.

The difference in mean AUC/time between the two treatment groups will be calculated as the mean Active AUC/time – the mean Standard of Care AUC/time, such that a positive difference indicates that the Active Treatment group had a larger mean AUC/time based on Change in KOOS JR. score than the Standard of Care Treatment group, while a negative value indicates the opposite. Because a positive Change in the KOOS JR. score is indicative of pain relief, a positive difference between treatment groups reflects a positive outcome for this endpoint.

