Let  $\mu_{2,\text{Active}}$  and  $\mu_{2,\text{SOC}}$  denote the true mean AUC/time based on the Change from Baseline in KOOS JR. score from the Baseline visit through the six-week visit for the active and standard of care treatments, respectively. Then the null and alternative hypotheses for the test for non-inferiority for this endpoint are as follows:

$$H_0: \mu_{2,\text{SOC}} - \mu_{2,\text{Active}} \geq \delta$$

$$H_1: \mu_{2,SOC} - \mu_{2,Active} < \delta,$$

where the non-inferiority margin  $\delta=14$ .

Missing KOOS JR. data will be imputed using multiple imputation methods. First, the relatively uncommon, non-monotone missing data will be imputed using the MCMC option of SAS® PROC MI. The imputation model will include a term for treatment and the KOOS JR. score at visits 1, 4, 5, and 6. Second, the monotone missing values will be imputed using the chained equation method by SAS® PROC MI option MONOTONE REG. For each subject within each imputed dataset, the value of the endpoint will then be determined. The imputed data sets will each be analyzed to obtain the difference in means between treatments and the corresponding standard error, and the results will be summarized using PROC MIANALYZE (with THETA0=14, the non-inferiority margin, in the PROC MIANALYZE statement). The null hypothesis will be tested using a one-sided t-test. One of the secondary objectives of the study is to show that, over the 6-week post-TKA period, the Active Treatment group has similar levels of pain and functioning as compared to the Standard of Care Treatment group. This objective will be met if the t-test for non-inferiority is statistically significant using a 0.025 level of statistical significance.

There is one item in the KOOS JR. scale (Knee Twisting/Pivoting) with a large number of missing responses. Prior to undergoing multiple imputation, missing values for this item will be imputed by performing a linear regression (SAS PROC GLM) on the other 6 KOOS JR. items and imputing the Knee Twisting/Pivoting score for each patient with a missing value based on the estimated linear regression line. At baseline this imputation will be performed across treatment arms; at post-baseline time points the imputation will be performed by treatment arm.

Change in NRS for Pain scores and TUG test scores from the Baseline visit to each post-baseline visit will be calculated for each subject as:

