(2) p-value from a two-sided, two-sample t-test, testing the null hypothesis that the iovera and Standard of Care means are equal versus the alternative hypothesis that they are unequal.

(3) p-value from a two-sided, paired t-test, testing the null hypothesis that the true mean equals 0.

(4) p-value from a one-sided, two-sample t-test, testing the null hypothesis that the iovera mean is less than or equal to the Standard of Care mean versus the alternative hypothesis that the iovera mean is greater than the Standard of Care mean.

Table 3

KOOS JR.  
ITT POPULATION

Parameter	Visit	Statistic	Iovera (N=xx)		Standard of Care (N=xx)		Difference in Mean Change from Baseline (Iovera - Standard of Care) and 95% CI (1)
			Value	Change from Baseline	Value	Change from Baseline	
Overall Score	Screening (Baseline)	n	xx		xx		
		Mean	xx.x		xx.x		
		Median	xx.x		xx.x		
		SD	xx.x		xx.x		
		Minimum - Maximum	xx - xx		xx - xx		
	72 Hours Post-op	95% CI for Mean (1)	(xx.x, xx.x)		(xx.x, xx.x)		
		n	xx	xx	xx	xx	
		Mean	xx.x	xx.x	xx.x	xx.x	xx.x (xx.x, xx.x)
		Median	xx.x	xx.x	xx.x	xx.x	
		SD	xx.x	xx.x	xx.x	xx.x	
	2 Weeks Post-op 6 Weeks Post-op 12 Weeks Post-op	Minimum - Maximum	xx - xx	xx - xx	xx - xx	xx - xx	
		95% CI for Mean (1)	(xx.x, xx.x)	(xx.x, xx.x)	(xx.x, xx.x)	(xx.x, xx.x)	
		...	...	...	...	...	...
		...	...	...	...	...	...
		...	...	...	...	...	...
AUC/time for Change from Baseline in Overall Score	Baseline through 72 Hours Post-op	n	xx		xx		
		Mean	xx.xx		xx.xx		xx (x.x, x.x)
		Median	xx.xx		xx.xx		
		SD	xx.xx		xx.xx		
		Minimum - Maximum	xx.x - xx.x		xx.x - xx.x		
	Baseline through 2 Weeks Post-op 6 Weeks Post-op 12 Weeks Post-op	95% CI for Mean (1)	(xx.xx, xx.xx)		(xx.xx, xx.xx)		
		p-value (2)	x.xxxx		x.xxxx		
		p-value (3)				x.xxxx	
		...	...	...	...	...	...
		...	...	...	...	...	...

Program Name:

Creation date, time

Note: Change from baseline = Post-baseline value - Baseline value, so that a positive change value indicates a positive outcome. Missing overall scores were imputed using multiple imputation methods.

Koos JR. normalized scores range from 0 (extreme symptoms) to 100 (no symptoms).

(1) Confidence interval based on the t-distribution.

(2) p-value from a two-sided, paired t-test, testing the null hypothesis that the true mean equals 0.

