(3) p-value from a one-sided, two-sample t-test, testing the null hypothesis that the Standard of Care mean minus the iovera mean is greater than or equal to the non-inferiority margin of 14 versus the alternative hypothesis that the difference in means is less than 14.

[figure not shown]

Table 5

TIMED GET UP AND GO (TUG) TEST  
ITT POPULATION

Parameter	Visit	Statistic	Iovera (N=xx)	Standard of Care (N=xx)		Difference in Mean Change from Baseline (Iovera - Standard of Care) and 95% CI (1)
			Value	Change from Baseline	Value	
TUG Time (seconds)	Screening (Baseline)	n (% of subjects)	xx (xx.x)		xx (xx.x)	
		Mean	xx.x		xx.x	
		Median	xx.x		xx.x	
		SD	xx.x		xx.x	
		Minimum - Maximum	xx - xx		xx - xx	
	2 Weeks Post-op	95% CI for Mean (1)	(xx.x, xx.x)		(xx.x, xx.x)	
		n (% of subjects)	xx (xx.x)	xx	xx (xx.x)	xx
		Mean	xx.x	xx.x	xx.x	xx.x
		Median	xx.x	xx.x	xx.x	xx.x
		SD	xx.x	xx.x	xx.x	xx.x
	6 Weeks Post-op 12 Weeks Post-op	Minimum - Maximum	xx - xx	xx - xx	xx - xx	xx - xx
		95% CI for Mean (1)	(xx.x, xx.x)	(xx.x, xx.x)	(xx.x, xx.x)	(xx.x, xx.x)
		...	...	...	...	...
		...	...	...	...	...
		...	...	...	...	...
AUC/time for Change from Baseline in TUG time	Baseline through 2 Weeks Post-op	n	xx		xx	
		Mean	xx.xx		xx.xx	x.x (x.x, x.x)
		Median	xx.xx		xx.xx	
		SD	xx.xx		xx.xx	
		Minimum - Maximum	xx.x - xx.x		xx.x - xx.x	
	6 Weeks Post-op 12 Weeks Post-op	95% CI for Mean (1)	(xx.xx, xx.xx)		(xx.xx, xx.xx)	
		p-value (2)	x.XXXX		x.XXXX	
		p-value (3)				x.XXXX
		...	...	...	...	...
		...	...	...	...	...

Program Name:

Creation date, time

Note: Change from baseline = Baseline value - post-baseline value, so that a positive change value indicates a positive outcome.

(1) Confidence interval based on the t-distribution.

(2) p-value from a two-sided, paired t-test, testing the null hypothesis that the true mean equals 0.

(3) p-value from a one-sided, two-sample t-test, testing the null hypothesis that the iovera mean is less than or equal to the Standard of Care mean versus the alternative hypothesis that the iovera mean is greater than the Standard of Care mean.

Table 6.1

OPIOID CONSUMPTION: TOTAL DAILY MORPHINE EQUIVALENT (TME)  
ITT POPULATION

Parameter	Time Period	Statistic	Iovera (N=xx)	Standard of Care (N=xx)	Difference between Treatments (Standard of Care - Iovera) and 95% CI (1)
TME	TKA to 72 Hours Post-op	n	xx	xx	
		Mean	xx.x	xx.x	xx.x (xx.x, xx.x)
		Median	xx.x	xx.x	
		SD	xx.x	xx.x	
		Minimum - Maximum	xx - xx	xx - xx	

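### The KOOS JR. non-inferiority margin of 14, set for AUC/time through 6 weeks, is reused unchanged for AUC/time through 72 hours, where it is generally not a 14-point test

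*SAP*

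**What the plan says.** SAP 8.2 (and Protocol 10.4.2) defines the key secondary endpoint as the trapezoidal area under the KOOS JR. change scores through the 6-week visit, divided by the days from TKA to that visit. The area is built "at the following time points: Baseline (change=0), 72 hours, 2 weeks, and 6 weeks post-TKA". The margin of 14 is set for this endpoint, and the SAP implements it "with THETA0=14, the non-inferiority margin, in the PROC MIANALYZE statement".

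SAP 8.4, Other Analyses, extends the AUC/time analyses to the horizons "through 72 hours post-TKA (KOOS JR. and NRS for Pain only), 2 weeks post-TKA and 12 weeks post-TKA" and says that they "will be analyzed in the same manner as described in Section 8.2 for the AUC/time endpoints through 6 weeks post-TKA". It gives no separate margin for any horizon.

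The Table 3 shell has a row group headed "AUC/time for Change from Baseline in Overall Score", beginning with Baseline through 72 hours. The block carries p-value (3), whose footnote tests the null hypothesis that "the Standard of Care mean minus the iovera mean is greater than or equal to the non-inferiority margin of 14", again without distinguishing horizons. The table layout is broken in the text available, but SAP 8.4 leads to the same reading by itself.

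The SAP does not say on which day the zero-change point sits. SAP 8.2 runs the area from the Baseline visit, SAP 5.8 takes Baseline from Screening, and Protocol 9.3 puts Screening at Day -30 to Day -1. The divisor nevertheless starts at TKA. SAP 5.9 bases analyses on nominal visits, but no nominal day is given for Baseline.

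**The concern.** A margin on AUC/time corresponds to a margin in KOOS JR. points only through the trapezoid weights, and these depend on the horizon. Over 6 weeks they nearly sum to one, so 14 on AUC/time is close to a constant 14-point deficit. Over 72 hours there is a single post-operative value joined by a straight line to an assumed zero, so the zero start dominates the result.

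The early window is one that readers will examine. Under Protocol 9.6 the control arm may receive periarticular infiltration and the iovera arm may not, so the arms differ in perioperative analgesia by design. A significant non-inferiority p-value at 72 hours, labelled with the trial's own margin, could be taken as evidence that early pain and function were comparable when the deficit was as large as 14 points.

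**Working it through.** **Inputs.** From the documents: margin 14; one-sided 0.025; about 60 per arm (SAP 3.4); nominal days 3, 14, 42 and 84; divisor counted from TKA. Assumed: the SD of the 72-hour KOOS JR. change, equal in both arms, varied from 15 to 30.

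**The plan's own figures.** No sample size, power, SD or derivation of the margin is given for any KOOS JR. test, so there is no KOOS JR. figure to reproduce. The only computed design figure is 57 per group for the opioid endpoint. The SAP inputs (difference 12.0, SDs 18.2 and 26.0) give 56 by the Satterthwaite t-test and 80.7% power at 57, so that figure is consistent to within one subject per group.

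**Step 1: zero point at TKA (Day 0).** Through 72 hours the area is 0.5 × change × days. Dividing by days leaves 0.5 × change, whatever the actual visit day. More generally, a constant deficit D from 72 hours onward gives AUC/time = D × (T − 1.5)/T at horizon T days.

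| Horizon | (T − 1.5)/T | Constant deficit equal to 14 |
|---|---|---|
| 72 h (T = 3) | 0.500 | 14/0.500 = 28.0 |
| 2 weeks (14) | 0.893 | 15.7 |
| 6 weeks (42) | 0.964 | 14.5 |
| 12 weeks (84) | 0.982 | 14.3 |

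Only the 72-hour horizon is materially different. For scale, SAP Appendix 1 converts raw scores 5 and 17 to 73.342 and 44.905, a gap of 28.4 interval points for 12 of the 28 raw points.

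**Step 2: chance of passing under Day 0.** A true 72-hour deficit d becomes d/2 on AUC/time, with standard error (SD/2) × √(2/60). The pass probability comes from the noncentral t with 118 df and noncentrality (14 − d/2)/SE. Example at SD 20 and d = 14: SE = 10 × 0.1826 = 1.826, and 7/1.826 = 3.83.

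| SD of 72-h change | d = 14 | d = 20 |
|---|---|---|
| 15 | 99.9% | 83% |
| 20 | 96.7% | 58% |
| 25 | 86.0% | 41% |
| 30 | 71.7% | 30% |

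Simulation with 20,000 runs agrees for d = 14 (99.9%, 96.7% and 85.5% at SD 15, 20 and 25). With 57 per arm, SDs of 15, 20 and 25 give 99.9%, 96.0% and 84.2%. A direct test of the 72-hour change against 14 would pass a true 14-point deficit 2.5% of the time at any SD.

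**Step 3: area started at Screening, s days before TKA, divisor still 3 days.** The factor is 0.5 × (3 + s)/3 = (3 + s)/6, and the effective margin is 14 divided by it. For simplicity all subjects are given the same s.

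| Screening day | Factor | Effective margin | Pass at d = 14, SD 20 |
|---|---|---|---|
| −1 | 0.667 | 21.0 | 47.7% |
| −3 | 1.000 | 14.0 | 2.5% |
| −7 | 1.667 | 8.4 | below 0.1% |
| −30 | 5.500 | 2.5 | below 0.1% |

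In practice s varies by subject, so on this reading there is no single effective margin.

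**The case against.** The strongest reply is that the 28-point figure is conditional. Read literally, the area starts at the Screening-day Baseline. Protocol 9.5 puts the iovera visit 5 ± 2 days before TKA, and Screening may be on that day but not after it. An on-schedule iovera subject therefore has s of at least 3, and there is no halving in that arm. This stands: a reader might infer that the plan uses a 28-point margin outright, and the documents do not settle that. Day 0 is the more coherent reading because the divisor starts at TKA. The alternative does not rescue the p-value, since its effective margin equals 14 only for Screening on Day -3.

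Second, nothing in either document makes 14 points of change at 72 hours the limit of acceptability, and the 14 itself has no stated derivation. This also stands. The 2.5% comparison shows what a 14-point test of the 72-hour change would do; it is not an error rate that the plan promised for that window.

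Third, no conclusion of the trial depends on this test. It sits under Other Analyses, the fixed sequence covers the 6-week key secondary, and the objective on comparable pain and function is tied to the 6-week period. Table 3 also prints the undiluted 72-hour difference in mean change. With a true 14-point deficit its expected 95% interval, iovera minus control, is about −14 ± 1.980 × 20 × 0.1826 = (−21.2, −6.8) at SD 20, which excludes zero. An attentive reader would therefore see the deficit. These facts limit the consequence, but one table could still show that interval beside a significant non-inferiority p-value.

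Finally, a reader might infer that a 14-point deficit would pass almost every time. That needs an SD of about 21 or less (95% or more at 60 per arm), which the documents do not supply.

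**Conclusion.** The point holds in a limited form. SAP 8.4 and Table 3 carry the 6-week margin of 14 to 72 hours, where it generally does not correspond to 14 KOOS JR. points. With the zero point at TKA it amounts to 28 points of 72-hour change, and a true 14-point deficit would pass most of the time over the SD range examined. With the area started at Screening it can be looser or much stricter than 14, depending on the screening day.

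The pass rates rest on Day 0 placement, 60 per arm and assumed SDs. The 2-, 6- and 12-week horizons are not materially affected under Day 0. A reader should not infer that formal study success, the primary analysis or the key secondary test is compromised. This is a recommended correction to a supporting output that could mislead.

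**What to change.** 1. In SAP 8.4, exclude the 72-hour horizon from the KOOS JR. non-inferiority test, and remove p-value (3) from the Baseline-through-72-hours block of Table 3.
2. Interpret the 72-hour window from the difference in mean change and 95% confidence interval already printed in Table 3. Reading it against 14 points of change should be a descriptive reference only.
3. State in footnote (3) that the margin of 14 was set for AUC/time through 6 weeks.
4. State in SAP 8.2 that the area starts with change = 0 at TKA (Day 0).

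If the sponsor wants to keep an AUC/time test at 72 hours, THETA0=7 is the same test as 14 points of 72-hour change, but only under Day 0 placement. It should be used only if a 14-point margin at 72 hours is justified.

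The cost is a few sentences and one table-shell edit, with no new data. The downside is that the 72-hour non-inferiority p-value is lost or, under Day 0 with THETA0=7, becomes harder to pass.

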## **9.0 SAFETY ANALYSES**

All adverse event analyses will be performed on the Safety Population.

The summary of AEs will be limited to treatment emergent AEs. For AEs with a missing start date, the AE will be considered treatment emergent unless there is additional information indicating that the AE started prior to study treatment.

Adverse events (AEs) will be coded using the Medical Dictionary for Regulatory Activities (MedDRA). Treatment-emergent AEs (TEAEs) are defined as any adverse event with onset on or after study treatment begins or any adverse event already present at baseline that worsens in severity. For AEs with missing start dates, the AE will be considered treatment-emergent unless there is additional information indicating that the AE started prior to study treatment. Only treatment emergent AEs will be summarized.

The number and percentage of subjects with at least one TEAE, at least one iovera procedure-related TEAE, at least one iovera device-related TEAE, at least one opioid use related TEAE, at least one serious TEAE, and at least one TEAE leading to study withdrawal will be presented by treatment group. AEs that are definitely, probably, or possibly related, or for which the relationship is missing, will be considered related.

The number and percentage of subjects having a TEAE in each System Organ Class (SOC) and having each individual type of adverse event (Preferred Term) will be presented. TEAEs will also be summarized at the event level by SOC/Preferred Term and severity. This will be done for all TEAEs, iovera procedure related TEAEs, iovera device related TEAEs, and opioid use related TEAEs.

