10.4.4 Safety

Adverse events (AEs) will be coded using the Medical Dictionary for Regulatory Activities (MedDRA). Treatment-emergent AEs (TEAEs) are adverse events with onset after study treatment begins and that are not present at baseline or, if present at baseline, have worsened in severity. For AEs with missing start dates, the AE will be considered treatment-emergent unless there is additional information indicating that the AE started prior to study treatment. Only treatment emergent AEs will be summarized.

The number and percentage of subjects with at least one TEAE, at least one device-related TEAE, at least one serious TEAE, at least one serious adverse device effect, at least one unanticipated serious adverse device effect, at least one anticipated serious adverse device effect, and at least one TEAE leading to study withdrawal will be presented by treatment group. AEs that are definitely, probably, or possibly related to the device, or for which the relationship to the device is missing, will be considered device-related. TEAEs will be summarized at the subject level by MedDRA system organ class (SOC) and preferred term using frequencies and percentages. TEAEs will also be tabulated at the event level by severity and by relationship to the device for each treatment group.

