### **3.5 Changes to the Protocol-Specified Analyses**

For the analyses of the primary effectiveness endpoint and the first secondary effectiveness endpoint, missing data will be imputed using multiple imputation methods. The protocol states that t-tests will be performed on the imputed datasets and the results will be summarized using PROC MIANALYZE. Instead, the difference in means between treatments and the corresponding standard error will be obtained for each imputed dataset and PROC MIANALYZE will be used to summarize the results and produce t-tests.

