		95% CI for Mean (1)	(xx.x, xx.x)	(xx.x, xx.x)	
	72 Hours Post-op to 2 Weeks Post-op	n	xx	xx	
		Mean	xx.x	xx.x	xx.x (xx.x, xx.x)
		Median	xx.x	xx.x	
		SD	xx.x	xx.x	
		Minimum - Maximum	xx - xx	xx - xx	
		95% CI for Mean (1)	(xx.x, xx.x)	(xx.x, xx.x)	
	2 Weeks Post-op to 6 Weeks Post-op	...	...	...	...
	6 Weeks Post-op to 12 Weeks Post-op	...	...	...	...
	Hospital Discharge to 2 Weeks Post-op	n	xx	xx	
		Mean	xx.x	xx.x	xx.x (xx.x, xx.x)
		Median	xx.x	xx.x	
		SD	xx.x	xx.x	
		Minimum - Maximum	xx - xx	xx - xx	
		95% CI for Mean (1)	(xx.x, xx.x)	(xx.x, xx.x)	
	Hospital Discharge to 6 Weeks Post-op	p-value (2)			x.xxxx
		...	...	...	...
		...	...	...	...

Program Name:

Creation date, time

Source: Listing 4

Note: Missing pill count data were imputed using multiple imputation methods.

(1) Confidence interval based on the t-distribution.

(2) p-value from a one-sided, two sample t-test, testing the null hypothesis that the true iovera mean is greater than or equal to the true Standard of Care mean versus the alternative hypothesis that the true iovera mean is less than the true Standard of Care mean.

Table 6.1 will be repeated in the following tables:

Table 6.2

OPIOID CONSUMPTION: TOTAL DAILY MORPHINE EQUIVALENT (TME):  
EXCLUDES DISCONTINUATIONS DUE TO ADVERSE EVENTS  
ITT POPULATION

Table 7.1

OPIOID CONSUMPTION: TOTAL DAILY MORPHINE EQUIVALENT (TME)  
PER PROTOCOL POPULATION

Table 7.2

OPIOID CONSUMPTION: TOTAL DAILY MORPHINE EQUIVALENT (TME):  
EXCLUDES DISCONTINUATIONS DUE TO ADVERSE EVENTS  
PER PROTOCOL POPULATION

*Programming note: for Tables 6.2 and 7.2, please add Listing 2.1 to Source.*

Table 8.1

TREATMENT EMERGENT ADVERSE EVENTS (TEAEs): OVERVIEW (SUBJECT LEVEL)  
SAFETY POPULATION

Parameter	OCS (N=xx) n (%)	Standard of Care (N=xx) n (%)
At least one TEAE	xx (xx.x)	xx (xx.x)
At least one iovera procedure-related TEAE (1)	xx (xx.x)	-
At least one iovera device-related TEAE (1)	xx (xx.x)	-
At least one opioid use related TEAE (1)	xx (xx.x)	xx (xx.x)
At least one serious TEAE	xx (xx.x)	xx (xx.x)
At least one TEAE leading to study withdrawal	xx (xx.x)	xx (xx.x)

Program Name:

Creation date, time:

Source: Listing 2.1

Note: Percentages are calculated based on the number of subjects in the ITT Population.

(1) Adverse events that are definitely, probably, or possibly related, or for which the relationship is missing, are considered related.

Table 8.2

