**Listing 2.1**

**ADVERSE EVENTS (AEs)**  
**SAFETY POPULATION**  
**Part 2 of 3**

Treatment Group	Subject Number	Event	Severity	Reported as SAE? (#1)	If 'Yes' in #1, Reason	Action(s) Taken	Study Exit due to this AE?
XXXXXXXX	XXX	XXXXXXXXXX	XXXXXXXX	XXX	XXXXXXXXXX	XXXX, XXXXXX	XXX

---

Program Name:

Creation date, time

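### SAP 9.0 and Table 8.1 omit the by-arm counts of serious, unanticipated and anticipated serious adverse device effects that Protocol 10.4.4 specifies, and SAP 3.5 does not record the change

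*SAP*

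**What the plan says.** Protocol 10.4.4 lists the subject-level safety counts to be shown for each arm. Besides any TEAE, device-related TEAEs, serious TEAEs and TEAEs leading to withdrawal, it names "at least one serious adverse device effect, at least one unanticipated serious adverse device effect, at least one anticipated serious adverse device effect". It then adds an event-level summary: "TEAEs will also be tabulated at the event level by severity and by relationship to the device for each treatment group". Protocol 11.2 defines the three classes. A SADE is a device effect with a serious outcome; it is unanticipated or anticipated according to whether the sponsor's risk analysis report already identifies it.

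SAP 9.0 replaces the subject-level list with one that ends "at least one opioid use related TEAE, at least one serious TEAE, and at least one TEAE leading to study withdrawal will be presented". It adds procedure-related and opioid-related TEAEs and leaves out the three device-effect classes. The Table 8.1 shell follows it, with separate rows such as "At least one serious TEAE" and "At least one TEAE leading to study withdrawal". At event level, SAP 9.0 asks for system organ class, preferred term and severity, for all TEAEs and for the procedure-, device- and opioid-related subsets.

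SAP 3.5, headed "Changes to the Protocol-Specified Analyses", describes one change: how results from the imputed data sets are combined.

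**The concern.** The protocol sets up these classes and gives them consequences. Under Protocol 14.6 the sponsor must decide for each serious event whether it is a USADE, and must terminate the investigation, or the parts concerned, if a USADE presents an unreasonable risk. A reader of the study report would therefore expect to find how many iovera subjects had a serious device effect and whether any was unanticipated. A programmer who follows the SAP exactly will not produce those counts, and nothing in the SAP tells the reader that the protocol asked for them. The trial is unblinded (SAP 3.3), and SAP 8.2 already remarks on the extent of missing responses to one questionnaire item, so some data had been seen when that text was written. That implies nothing about motive, but it is a good reason to record any departure in a protocol-specified safety summary.

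**Working it through.** No stated figure has to be reproduced. The check is a comparison of lists, followed by what can and cannot be recovered from the planned output.

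**Step 1. Subject-level counts.**

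| Count | Protocol 10.4.4 | SAP 9.0 and Table 8.1 |
|---|---|---|
| Any TEAE | yes | yes |
| Device-related TEAE | yes | yes |
| Serious TEAE | yes | yes |
| TEAE leading to withdrawal | yes | yes |
| SADE | yes | no |
| USADE | yes | no |
| ASADE | yes | no |
| Procedure-related TEAE | no | yes |
| Opioid-related TEAE | no | yes |
| Total | 7 | 6 |

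Four are kept and three dropped (4 + 3 = 7); two are added (4 + 2 = 6). Tables 8.2 to 9.6 do not supply the missing three. The SAP's list of tables skips some other numbers (4, 10, 12 to 14), which may have been withheld, but the text of SAP 9.0 is unbroken and describes no further safety table.

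**Step 2. Is the change recorded?** SAP 3.5 covers only the imputation analysis. SAP 8.4 separately discloses that certain pain comparisons were not pre-planned, so the SAP does flag departures elsewhere. It says nothing about this one.

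**Step 3. What Table 8.1 alone reveals.** Serious and device-related TEAEs are separate rows. The number of subjects with a SADE is at most the smaller of the two counts. It can be zero even for a subject who is in both rows, because the serious event and the device-related event may be different events. For illustration, assume 3 of 60 iovera subjects with a serious TEAE and 5 of 60 with a device-related TEAE (60 is the planned arm size; the 3 and 5 are assumptions):

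- upper bound: min(3, 5) = 3 subjects, 3/60 = 5.0%
- lower bound: 0 subjects, 0/60, with exact two-sided 95% upper limit 1 − 0.025^(1/60) = 6.0%

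Table 8.1 would be identical for 0, 1, 2 or 3 subjects with a SADE. The ambiguity disappears if either row is zero. Table 9.4 does not resolve it, because severity as graded in Protocol Table 3 is not seriousness as defined in Protocol 11.2.

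**Step 4. What the listings add.** Listing 2.1 Part 2 has a field for whether each event was reported as an SAE. Part 3 gives its relatedness to the iovera device and to the iovera procedure. Both parts carry treatment group, subject number and event. Joining them identifies each SADE, so the ambiguity in step 3 can be resolved by hand. No table or listing shown has a field for anticipated or unanticipated status, so the USADE/ASADE split cannot be derived unless there are no SADEs.

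**Step 5. Event-level relationship.** Tables 9.2 and 9.4 give procedure-related and device-related events by severity, and Table 8.3 gives all events. Related versus all is therefore available. The split across the five grades of Protocol Table 4 is not.

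**The case against.** The strongest reply is that little information is lost. SADEs can be read from Listing 2.1; USADE and ASADE are only the two parts of SADE, so counting three losses out of seven makes the gap look larger than it is; and the SAP's stated safety endpoint is simply all TEAEs. The sponsor's duty to assess each serious event stands whatever the SAP tabulates. This largely holds, and it is why the point is minor. It does not answer the mismatch itself: the protocol specified tabulated counts by arm, the SAP does not provide them, and no reason is given.

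A second reply is that the listing shells as read may be incomplete. Table 9.5 cites Listing 2.1 as its source for opioid-related events, yet Part 3 shows no opioid-relatedness column. That is fair, so the absence of an anticipated/unanticipated field can be claimed only for the output shown. It does not affect the omission from SAP 9.0.

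A reader might infer three stronger things:

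- That the safety output cannot tell whether a serious event was a device effect. Listing 2.1 can.
- That tabulation by relationship has been abandoned. Tables 9.2 and 9.4 keep it as related events.
- That the counts were removed deliberately, or that unanticipated effects would go undetected. The documents give no reason for the omission, and Protocol 14.6 keeps detection and reporting with the sponsor.

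**Conclusion.** The point holds as an unrecorded mismatch between protocol and SAP in planned safety reporting. All three device-effect counts are missing from SAP 9.0 and Table 8.1. One of them (SADE) can be rebuilt by cross-reading Listing 2.1. The other two cannot be rebuilt from any output shown, though this is moot if there are no SADEs. At event level, only the breakdown by relationship grade is lost. Safety surveillance, the effectiveness analyses and the sample size are unaffected. The conclusion rests on the unredacted text of SAP 9.0 and SAP 3.5 and on the shells as they can be read; the 3 of 60 and 5 of 60 are illustrative only. Severity: minor.

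**What to change.** - Add SADE, USADE and ASADE rows to SAP 9.0 and Table 8.1.
- Derive SADE from the SAE flag and device relatedness on the same event record, not from two subject-level flags. State whether procedure-related events count, since the SAP separates device from procedure, and whether a missing relationship is treated as related, as it is elsewhere in SAP 9.0.
- Take anticipated/unanticipated status from the sponsor's determination under Protocol 14.6 and show it as a column in Listing 2.1.
- Restore the event-level tabulation by relationship grade, or list its removal in SAP 3.5 with a reason. Any of the three counts left out on purpose should be recorded there too.

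The cost is a few lines of SAP text, three table rows, one listing column and, if restored, one event-level table. Seriousness and relatedness are already in the listing. The only extra work is that the sponsor's USADE determination may sit outside the clinical database and have to be transferred into the analysis data. In return the report can state the numbers of serious and unanticipated device effects outright, including when they are zero.
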